1 INTRODUCTION

The purpose of this Statistical Analysis Plan (SAP) is to provide a description of the statistical methods to be implemented for the analysis of data from the study with protocol number CYP003 for Phase 1b only. Due to the termination after Phase 1b of the study, this SAP will contain a full report on safety endpoints and an abbreviated selection of efficacy endpoints. The SAP will be finalized prior to database lock. Any deviations from the SAP after database lock will be documented in the final Clinical Study Report (CSR).

2 STUDY OVERVIEW

2.1 Study Objectives of Phase 1b only

This section describes the abbreviated study objectives for Phase 1b only.

2.1.1 Primary Objective

• Confirm the recommended CyPep-1 dose (20 mg every 2 weeks [Q2W]) when administered by intra-tumoral (IT) injection in combination with pembrolizumab.

2.1.2 Secondary Objective

• Evaluate the PK of CyPep-1 in combination with pembrolizumab.

2.1.3 Explorative Objective

- Analyze changes in biomarkers and tumor kinetics associated with the mode of action of CyPep-1 and pembrolizumab by tumor biopsy from injected lesions.
- Expand evaluation of anti-tumor activity of CyPep-1 and pembrolizumab.

2.2 Study Endpoints in Phase 1b only

This section describes the abbreviated study endpoints for Phase 1b only. Any pharmacokinetic analyses will be described in a separate document.

2.2.1 Primary Endpoints

- Incidence, frequency, and seriousness of Treatment-emergent adverse events (TEAEs);
- Incidence of dose-limiting toxicities (DLTs); and
- Changes from baseline in vital signs, body weight, 12-lead electrocardiogram (ECG) parameters, and laboratory assessments.

2.2.2 Secondary Endpoints

Plasma concentration-time profile of CyPep-1 and, if detectable, the following derived PK parameters:

• Area under the curve (AUC), Peak plasma concentration (C_{max}), Time to reach peak plasma concentration (T_{max}), clearance (CL), terminal half-life ($t_{1/2}$), and volume of distribution (VD).

2.2.3 Exploratory Endpoints

- Number and relative change of tumor infiltrating immune cells;
- Expression of selected immune cell biomarkers;
- Change from baseline in target tumor lesion size over time, overall, and by injected versus non-injected lesions;
- Maximum decrease from baseline in target tumor lesions, overall, and by injected versus non-injected lesions;
- Changes in new lesions treated with CyPep-1; and
- ORR according to Intratumoral-Response Evaluation Criteria in Solid Tumors (itRECIST).

2.3 Study Design

2.3.1 Overview

This is an open-label, multi-center, non-randomized Phase 1b/2a study. The Phase 1b portion of the study (the first 6 patients enrolled) will confirm the recommended CyPep-1 dose of 20 mg every 2 weeks (Q2W) in combination with pembrolizumab 400 mg every 6 weeks (Q6W).

The following 3 study arms will be included in the study:

- Arm A: Patients with advanced or metastatic Head and Neck Squamous Cell Carcinoma (HNSCC)
- Arm B: Patients with Melanoma
- Arm C: Patients with Triple-Negative Breast Cancer (TBNC).

Patients will receive intra-tumoral (IT) injections of a fixed concentration of CyPep-1 Q2W beginning at Cycle 1 Visit 1. Pembrolizumab will be administered intravenously (IV) at a fixed dose Q6W beginning at Cycle 1 Visit 1. Patients must be observed for 4 hours post injection for pharmacokinetic (PK) monitoring on Cycle 1 Day 15. The plasma concentration-time profile of CyPep-1 and, if detectable, the derived PK parameters will be assessed.

The dose-limiting toxicity (DLT) period for the Phase 1b portion of the study will be Cycle 1 (initial 6 weeks of study treatment). After the first 6 patients have completed the DLT period, the Data Monitoring Committee (DMC) and Sponsor will review safety and tolerability data prior to the enrollment of the patients into the Phase 2a portion of the study. If ≤2 DLTs are observed in the first 6 patients, then the recommended CyPep-1 dose will be confirmed and enrollment of the remainder of the patients should continue.

If >2 of the 6 patients develop a DLT at the recommended CyPep-1 dose level (5 mg/mL dose concentration), then the maximum tolerated dose (MTD) of CyPep-1 will be assumed to have been exceeded and dose de-escalation will be conducted to determine the MTD. At least 6 patients will be treated at CyPep-1 dose level -1 (2 mg/mL dose concentration). If necessary, due to >2 DLTs in the dose level -1 cohort, a further reduction to dose level -2 (0.5 mg/mL dose concentration) will be performed.

Dose de-escalation will proceed according to the following rules:

- If ≤2 out of 6 patients develop a DLT, the MTD will be declared; or
- If >2 out of 6 patients develop a DLT, the dose will be de-escalated to the next lower dose.

The MTD will guide confirmation, by agreement of the DMC and the Sponsor, of a recommended Phase 2 dose (RP2D). The RP2D may be equivalent to the MTD or may be a dose below the MTD and will be dependent on an acceptable tolerability profile and manageable adverse events (AEs). The patients from Phase 1b will continue to the Phase 2a portion of the study. After the DMC reviews the safety data, feedback will be provided to the Sponsor regarding the further conduct of the study.

For detailed definition of DLT, please refer to the study protocol Section 3.1.1.1.

2.3.2 Study Drug

The overall study treatment regimen is defined as IT CyPep-1 in combination with IV pembrolizumab.

2.3.3 CyPep-1

CyPep-1 will be administered Q2W as an IT injection. CyPep-1 will be administered through a needle, which should be redirected along multiple tracks to ensure even dispersion of CyPep-1 throughout the tumor lesion. On the visits that CyPep-1 and pembrolizumab are administered on the same day, CyPep-1 is to be administered 30 to 60 minutes after pembrolizumab infusion is completed. Refer to the Guidance for Intra-tumoral Administration of CyPep-1 study manual for more details.

The cumulative maximal injected volume of CyPep-1 will be 4 mL (cumulative maximal dose of 20 mg at the recommended 5 mg/mL concentration) per treatment day for each patient, and it may be divided for injection over 1 to 3 tumor lesions depending on tumor lesion sizeCyPep-1 dose modifications are not planned. In the event of CyPep-1-related excessive toxicity, administration of CyPep-1 may be delayed for no more than 7 days; and if delayed >7 days, then that dose will be omitted at the discretion of the Investigator with the approval of the Medical Monitor.

2.3.4 Pembrolizumab

The dose of pembrolizumab in combination with CyPep-1 will be 400 mg Q6W administered via a 30-minute infusion, beginning at Cycle 1 Visit 1. On the visits that CyPep-1 and pembrolizumab are administered on the same day, CyPep-1 is to be administered 30 to 60 minutes after pembrolizumab infusion is completed. Pembrolizumab may be administered up to 3 days before or after the scheduled Visit 1 of each cycle from Cycle 2 onward.

2.3.5 Sample Size Determination

The sample size for the Phase 1b portion of the study is based on practical determinations. The first 6 patients of the study are planned to be enrolled in the Phase 1b portion.

3 STATISTICAL METHODOLOGY

This section describes the statistical analyses to be conducted in relation to the primary, secondary, and exploratory objectives of the Phase 1b part of the study.

3.1 General Considerations

All analyses will be performed using SAS[®] Version 9.4. Unless explicitly stated, no formal hypothesis testing will be performed for this study. All variables will be analyzed by descriptive statistical methods. Confidence intervals (CIs) will be constructed at the 2-sided 95% confidence level where appropriate.

Comprehensive data listings of all data will be generated. By-patient data listings of all clinical trial data will include all enrolled patients.

3.1.1 Treatment Groups and Arms

In general, all summaries will be displayed in *Total* for Phase 1b. By-arm summaries will not be displayed given the small sample size in Phase 1b.

3.1.2 Analysis Day

Analysis day will be calculated from the date of first dose of CyPep-1. The day of the first dose of study drug will be Day 1, and the day immediately before Day 1 will be Day -1. There will be no Day 0.

3.1.3 Analysis Visits

Analysis visits will be based on the nominal scheduled visit (case report form [CRF] visit label).

In general, for by-visit summaries, data will be presented based on the scheduled visits. Visit windowing will not be used for handling unscheduled visits. Instead, all unscheduled visits will be assigned a visit name of "Unscheduled". Such visits will be included in data listings and will contribute to the derivation of best- or worst-case values where applicable.

3.1.4 Definition of Baseline

Unless specified otherwise, baseline is defined as the last non-missing measurement prior to the first dose of study drug (CyPep-1 or pembrolizumab).

3.1.5 Summary Statistics

Categorical data will generally be summarized with counts and percentages of patients. The denominator used for the percentage calculation will be clearly defined. Continuous data will generally be summarized with descriptive statistics including n (number of non-missing values), mean, median, standard deviation, minimum, and maximum.

3.1.6 Handling of Dropouts and Missing Data

In general, missing data values will be recorded as missing and will not be imputed for the statistical analysis unless specified otherwise.

For missing or partial AEs and concomitant medications (CM) dates, conservative conventions will be applied in order to assign the events to corresponding periods (e.g. treatment period to ensure that no TEAE is missed). AEs will be considered as treatment-emergent, and the medications will be considered as concomitant if the missing/partial dates cannot definitively exclude the treatment period. Handling incomplete dates (e.g., AE and concomitant medications) are described in Appendix E.

Treatment duration

For the calculation of treatment duration, the date of last study drug infusion should be consistent with that of the last dose on the dosing page of the electronic case report form (eCRF). If the date of last dose on the dosing page is missing on the eCRF, use the last available dose date on the dosing page of eCRF to calculate. The last infusion should be clearly recorded on eCRF and not be estimated by the date of returning remaining study drug.

Laboratory values

Unless otherwise specified, for laboratory values that are reported using a non-numeric qualifier (e.g., less than [<] or greater than [>] sign), the reported numeric values will be used for summary or analysis without the qualifier.

In some cases, when the White Blood Cells (WBC) count is too low, the WBC differentials may be difficult to detect and thus not reported by the lab. If the reported WBC count < 0.5*10^9/L, then the differentials such as absolute neutrophils value will be imputed as zero for both the lab value summary and the Common Terminology Criteria for Adverse Events (CTCAE) v5.0 grading. For example, absolute neutrophils value imputed as 0 would be considered as grade 4.

3.2 Analysis Populations

3.2.1 Full Analysis Set

The Full Analysis Set (FAS) will include all patients who receive an injection of CyPep-1. The FAS will be used in the analysis of efficacy and exploratory endpoints.

3.2.2 Safety Analysis Set

The Safety Analysis Set (SAS) will include all patients who receive at least 1 injection of CyPep-1 or at least 1 administration of pembrolizumab. The SAS will be the basis of safety analyses.

3.3 Patient Data and Study Conduct

3.3.1 Patient Disposition

Data tabulations will be summarized for Phase 1b for the following patient numbers:

- Screened
- Screen Failure
- Enrolled
- Treated (CyPep-1 and/or pembrolizumab)
- Discontinued from CyPep-1 or pembrolizumab
- Study completion
- Discontinued from the study

Reasons for treatment discontinuation and for study discontinuation will be summarized.

All disposition data will be listed by patient.

3.3.2 Protocol Deviations

Counts and percentages of patients with CSR reportable protocol deviations by deviation category will be summarized in total based on the Safety Analysis Set.

All protocol deviations will be listed by patient.

3.3.3 Analysis Populations

Counts and percentages of patients in each analysis population will be summarized in total based on all enrolled patients.

3.3.4 Demographic and Baseline Characteristics

Demographic and baseline characteristics will be summarized with descriptive statistics or counts and percentages of patients as appropriate for the Safety Analysis Set and the Full Analysis Set. If the two sets are identical, only one version of the table will be presented. The following demographic and baseline characteristics will be summarized:

- Age at informed consent (years) and age categories (<65 years, ≥65 years);
- Sex:
- Childbearing potential if female;
- Race:
- Ethnicity;
- Height (cm);
- Weight (kg); and
- Body mass index (BMI) (kg/m²).

All available demographic information will also be listed by patient for the Safety Analysis Set.

3.3.5 Primary Cancer History

Primary cancer history will be coded using the Medical Dictionary for Regulatory Activities (MedDRA) version 25.0. The following primary cancer history information will be summarized descriptively for the Safety Analysis Set.

- For Melanoma:
 - Type (Superficial spreading, Nodular, Lentigo maligna, Amelanotic, Acral lentiginous, Mucosal, Other);
 - o Tumor Stage at diagnosis (0, I, II, III, IIIA, IIIB, IIIC, IIID, IV, Other);
 - o BRAF (Wild type, mutated, not tested);
 - Grade (Well differentiated, Moderately differentiated, Poorly differentiated, Undifferentiated, Not Applicable, Unknown); and
 - o Tumor stage at trial entry (locally advanced, metastatic).

All cancer history data will be listed by patient for the Safety Analysis Set.

3.3.6 Medical History

Medical history will include an evaluation of past and present history of the systems and/or conditions. Medical history will be coded using the Medical Dictionary for Regulatory Activities (MedDRA) version 25.0.

All available medical history will be listed by patient for the Safety Analysis Set.

3.3.7 Prior & Concomitant Medications

All medications and therapies taken within 28 days prior to the Screening Visit until the Safety Follow-up Visit will be recorded in the eCRF. Prior medications include medications that were taken prior to and stopped before the first dose of the study treatment. Concomitant medications include medications that were taken on or after the first dose date of the study treatment until 30 days after the last dose of study treatment.

All prior and concomitant medications will be coded using the World Health Organization (WHO) Drug Dictionary (WHODrug Global B3, Version March 2022). Concomitant medications will be summarized by Anatomical Therapeutic Chemical (ATC) and preferred term in total for the Safety Analysis Set. For each medication, the ATC used in the summary is taken as the highest available level from among ATC1, ATC2, ATC3, and ATC4. That is, if ATC4 is available, it will be used as the ATC for the summary, but if not available then the next highest level will be used. Although a patient may have taken two or more medications, the patient is counted only once within each ATC and preferred term classification. The same patient may contribute to two or more preferred terms in the same ATC classification.

All prior and concomitant medication data will be listed by patient for the Safety Analysis Set.

3.3.8 Prior Cancer Treatment

Prior systemic cancer therapy will be coded using the World Health Organization (WHO) Drug Dictionary (WHODrug Global B3, Version March 2022).

The following prior cancer treatment status will be summarized descriptively for the Safety Analysis Set:

- prior systemic anti-cancer therapy (yes, no), type of prior systemic cancer therapy (neoadjuvant, adjuvant, maintenance, metastatic), and the best overall response to the last prior systemic anti-cancer therapy
- prior cancer radiation therapy (yes, no),
- prior cancer surgeries (yes, no)

All available prior cancer treatment data (including radiation therapy and surgery) will be listed by patient for the Safety Analysis Set.

3.3.9 Study Drug Exposure and Compliance

Duration of Treatment

The duration of treatment (in weeks) for CyPep-1 will be calculated as (the last dose date of CyPep-1 minus the first dose date of CyPep-1 + 14)/7.

The duration of treatment (in weeks) for pembrolizumab will be calculated as the (last dose date of pembrolizumab minus the first dose date of pembrolizumab + 42)/7.

Descriptive statistics will be provided for the treatment duration of CyPep-1 and pembrolizumab for the Safety Analysis Set. Note that the exposure calculation is intended to describe the length of time a patient was exposed to the study drug and therefore does not take study drug interruptions into account.

Total number of cycles initiated

For each patient, the total number of cycles initiated is defined as the total number of cycles that the patient took the study drug recorded on the eCRF(s) during the study. The total number of cycles initiated will be summarized descriptively. In addition, the number and percentage of patients with total number of cycles in the following categories will also be presented: 1 cycle, 2 cycles, 3 cycles, and ≥4 cycles.

Dosing Status

The number and proportion of patients with dose omissions (CyPep-1 and pembrolizumab), dose reductions (CyPep-1 and pembrolizumab), and dose interruptions (pembrolizumab only) will be summarized.

Dosing Intensity

The cumulative dose of (CyPep-1 and pembrolizumab) per patient across the treatment period is the sum of the actual dose (mg) the patient received.

The actual dose intensity will be calculated for each patient as follows:

- Dose intensity of CyPep-1 (mg/week) = cumulative dose of CyPep-1 (mg) /duration of treatment for CyPep-1(in weeks)
- Dose intensity of pembrolizumab (mg/week) = cumulative dose of pembrolizumab (mg) /duration of treatment for pembrolizumab (in weeks)

The overall relative dose intensity (%) for CyPep-1 and pembrolizumab will be calculated as (the actual dose intensity/planned dose intensity per protocol)*100%

All study drug administration data will be listed by patient and tabulated by study arm.

3.4 Efficacy Assessment

All efficacy analysis will be based on the Full Analyses Set (FAS).

The Investigator will assess tumor responses according to Response Evaluation Criteria in Solid Tumors (RECIST) 1.1 criteria, immune Response Evaluation Criteria in Solid Tumors (iRECIST) criteria and Intratumoral-Response Evaluation Criteria in Solid Tumors (itRECIST); see Appendices B, C, and D respectively. Efficacy evaluations will include the following: Local measurement of tumor lesions, radiological assessments, tumor biopsy, and peripheral cytokines.

Response (Complete response [CR] / partial response [PR], immune complete response [iCR] / immune partial response [iPR]) must be confirmed by a repeat assessment performed no less than 6 weeks after the criteria for response are first met. When stable disease (SD) or immune stable disease (iSD) is believed to be the best response, it must also meet the minimum interval of 6 weeks (42 days) from the start of the treatment. Best overall response (BOR) will be determined based on the overall visit responses from each RECIST and iRECIST assessment by the Investigator. BOR is defined as the best response designation (in the order of CR, PR, SD, progression of disease [PD] using RECIST, and in the order of immune complete response [iCR], immune partial response [iPR], immune stable disease [iSD], immune confirmed progression of disease [iCPD] and immune unconfirmed progression of disease [iUPD] using iRECIST) a patient has had following the first dose of study treatment, but prior to and including progression (PD for RECIST and iCPD for iRECIST) or the last evaluable assessment in the absence of disease progression. Patients with no evaluable assessments after the first study dose will be assigned to

the not evaluable (NE) category. The determination of the best overall response by RECIST 1.1, iRECIST and itRECIST is summarized in Appendices B, C, and D.

For patients with solid tumors who have evidence of disease progression at a post baseline tumor assessment (iUPD) and who remain on study treatment, repeat imaging studies are required within 4 to 8 weeks to assess for confirmation of disease progression. If unconfirmed at the next assessment, continue tumor assessments every 6 weeks (±7 days) until the earliest of any of the following: start of a new anticancer therapy, iRECIST confirmed progression of disease, withdrawal of consent by the patient, investigator decision to terminate treatment, sponsor termination of the study, pregnancy, loss to follow-up, or death.

Anticancer activity parameters that will be assessed include the determination of the following:

- Disease control rate (DCR) (CR+PR+SD) per RECIST v1.1 and iRECIST;
- Progression-free survival (PFS) per RECIST v1.1 and iRECIST; and
- Overall survival (OS) (for up to 26 months from Cycle 1 Visit 1).

3.4.1 Definition of Efficacy Endpoints

Disease Control Rate (DCR)

The Disease Control Rate per RECIST 1.1 is defined as the proportion of patients whose best overall response is CR, PR, or SD at ≥16 weeks.

 DCR = 100 x (Number of patients [CR+PR+SD]) / Total number of patients in Full Analysis Set

DCR per iRECIST (iDCR) is defined as the proportion of patients whose best overall response is iCR, iPR, or iSD at ≥16 weeks.

Disease assessments after the start of new anticancer therapy will be excluded from the determination of CR, iCR, PR, iPR, SD, or iSD.

Progression Free Survival (PFS):

PFS per RECIST 1.1 will be defined as the time from the first dose date of study drug to first observation of documented PD per RECIST 1.1 or death due to any cause within 12 weeks of last tumor assessment, per RECIST 1.1:

PFS (months) = (Event/censoring date – first dose date + 1)/30.4375

For patients who have not progressed and are still alive at time of data cutoff for study analysis or who are lost to follow-up, PFS will be right censored. The event or censoring date will be determined based on the conventions listed in **Table 3.1**.

Table 3.1: Progression Free Survival (PFS)

Situation	Date of event or censoring	Outcome
Death before first planned disease assessment	Date of death	Event

Death or disease progression between planned disease assessments	Date of death or first disease assessment showing disease progression, whichever occurs first	Event
No postbaseline disease assessments	Date of first dose	Censored
Initiation of alternate anticancer treatment before disease progression or death (without disease progression beforehand)	Date of last evaluable disease assessment prior to start of alternate anticancer treatment	Censored
Death or disease progression after missing two or more consecutively scheduled disease assessments	Date of last evaluable disease assessment visit without documentation of disease progression before the first missed visit	Censored
Alive and without disease progression	Date of last evaluable disease assessment	Censored

The PFS time will be derived based on scan/assessment dates and not visit dates to determine radiological progression. Assessments/scans contributing towards a particular visit may be performed on different dates. The following rules will be applied for this calculation:

- Date of radiological progression will be determined based on the earliest assessment/scan dates of the component that triggered the progression (PD using RECIST).
- When censoring a patient for PFS, the patient will be censored at the latest of the assessment/scan dates contributing to a particular overall visit assessment.

PFS per iRECIST (iPFS):

iPFS will be defined as the time from the first dose date of study drug to first observation of documented iCPD per iRECIST or death due to any cause within 12 weeks of last tumor assessment:

• iPFS (months) = (Event/censoring date – first dose date + 1)/30.4375

The iPFS time will be derived based on scan/assessment dates in the same manner as the PFS time derivation. To be counted as disease progression, the iUPD assessment must be confirmed as iCPD at the next iRECIST assessment. In the event that an iUPD response is assessed but the progression is not confirmed (e.g. a later assessment of iSD, iPR, or iCR is observed) then the initial iUPD will not be counted as an event for determination of iPFS. To be conservative, in the case that an assessment of iUPD is recorded and no subsequent evaluable iRECIST assessments are recorded then the iUPD event will be treated as confirmed disease progression.

For patients who have not progressed and are still alive at time of data cutoff for study analysis or who are lost to follow-up, iPFS will be right censored. The same censoring rules for PFS using RECIST 1.1 as specified in **Table 3.1** will be applied.

Overall Survival (OS)

OS is defined as the interval from the start of first study dose to death from any cause. Patients who are alive or lost to follow-up as of the data cutoff date will be censored at the date the patient was last known to be alive:

• OS (months) = (Death date/censoring date – first study dose date + 1)/30.4375

The last date known to be alive for each individual patient may be determined using, but not limited to, the following dates recorded on the eCRF:

- AE start and stop dates,
- Study treatment start and stop dates,
- Laboratory assessment dates,
- Dates of vital signs, physical examination, Eastern Cooperative Oncology Group (ECOG),
- Performance status, and electrocardiogram (ECG) assessments,
- Disease assessment dates,
- Start and stop dates of concomitant medications including procedures and alternative anticancer therapy, and
- Date patient last known to be alive on long-term follow-up.

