7.2 Radiological Assessment

A baseline radiology assessment will be performed within 4 weeks prior to Cycle 1 Visit 1 to identify injected lesions and non-injected lesions and these lesions will be assessed according to RECIST v1.1. Subsequent radiological assessments will be performed Q8W (±3 days) after the first dose of CyPep-1, according to RECIST v1.1, until the occurrence of confirmed PD as defined by iRECIST (Appendix D), start of a new anti-cancer treatment, pregnancy, death, withdrawal of consent, or end of study (approximately 26 months after the start of treatment). Tumor scans may be performed more frequently if clinically indicated. MRI or CT are the preferred scanning procedures to be used in this study. Selection of either MRI or CT should be based on individual patient considerations and local regulations and is at the Investigator's discretion. Once selected for each patient, the same scanning procedure should be used consistently at all remaining visits. Scans will be collected and held centrally for potential central radiologic review.

Scan timing should follow calendar days and should not be adjusted for delays in cycle starts.

A confirmatory radiological assessment is required 4 weeks after an initial radiological scan leading to an assessment of PD. If the PD is confirmed, the initial assessment of PD will be considered as the "first documented PD." If PD is not confirmed, the first measured PD will be disregarded and assessments should continue as per protocol (ie, the next radiological assessment will be performed after an 8-week interval).

If a patient discontinues study treatment without documented disease progression, every effort should be made to monitor disease status by continuing tumor scans Q8W from start of study treatment. Scans will be continued until occurrence of confirmed PD as defined by iRECIST (Appendix D), start of a new anti-cancer treatment, pregnancy, death, withdrawal of consent, or end of study (approximately 26 months after the start of treatment).

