On the confirmatory scans, the patient will be classified as progression confirmed (with an overall response of iCPD), or as showing persistent unconfirmed progression (with an overall response of iUPD), or as showing disease stability or response (stable disease [iSD]/partial response [iPR]/complete response [iCR]).

Confirmation of Progression

Progression is considered confirmed, and the overall response will be iCPD, if ANY of the following occurs:

- · Any of the factors that were the basis for the initial iUPD show worsening; or
 - For target lesions, worsening is a further increase in the sum of diameters of ≥5 mm, compared to any prior iUPD time point;
 - For non-target lesions, worsening is any significant growth in lesions overall, compared to a prior iUPD time point; this does not have to meet the "unequivocal" standard of RECIST v1.1; or
 - o For new lesions, worsening is any of these:
 - An increase in the new lesion sum of diameters by ≥5 mm from a prior iUPD time point;
 - Visible growth of new non-target lesions; or
 - The appearance of additional new lesions.
- Any new factor appears that would have triggered PD by RECIST v1.1.

Persistent iUPD

Progression is considered not confirmed, and the overall response remains iUPD, if:

None of the progression-confirming factors identified above occurs; AND

The target lesion sum of diameters (initial target lesions) remains above the initial PD threshold (by RECIST v1.1).

Additional scans for confirmation are to be scheduled 4 weeks to ≤8 weeks from the scans on which iUPD is seen. This may correspond to the next visit in the original visit schedule. The assessment of the subsequent confirmation scan will proceed in an identical manner, with possible outcomes of iCPD, iUPD, and iSD/iPR/iCR.

Resolution of iUPD

Progression is considered not confirmed, and the overall response becomes iSD/iPR/iCR, if:

None of the progression-confirming factors identified above occurs; AND

The target lesion sum of diameters (initial target lesions) is not above the initial PD threshold.

The response is classified as iSD or iPR (depending on the sum of diameters of the target lesions), or iCR if all lesions resolve.

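### SAP 3.4.1 runs iPFS to the confirmatory scan while Protocol 7.2 dates confirmed progression at the initial scan, and its 12-week death limit disagrees with Table 3.1 for deaths about 12 to 16 weeks after the last scan

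*SAP*

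**What the plan says.** **Date of an iPFS event.** In SAP 3.4.1, "iPFS will be defined as the time from the first dose date of study drug to first observation of documented iCPD per iRECIST" or to death. SAP Appendix C places iCPD at the repeat imaging: "On the confirmatory scans, the patient will be classified as progression confirmed (with an overall response of iCPD"). If iUPD persists there, the process continues: "Additional scans for confirmation are to be scheduled 4 weeks to ≤8 weeks from the scans on which iUPD is seen".

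The derivation paragraph in SAP 3.4.1 is built around the iUPD instead:
- To count as progression, "the iUPD assessment must be confirmed as iCPD at the next iRECIST assessment".
- If progression is not confirmed, the initial iUPD is not counted as an iPFS event.
- If "no subsequent evaluable iRECIST assessments are recorded then the iUPD event will be treated as confirmed disease progression".

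Protocol 7.2 has its own dating rule: "If the PD is confirmed, the initial assessment of PD will be considered as the" first documented progression.

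**Deaths.** Both the PFS and the iPFS definitions count a death from any cause only within 12 weeks of the last tumor assessment. Table 3.1 has no such limit. A death before the first planned assessment or between planned assessments is an event. A death after two or more consecutive missed scheduled assessments is censored at the last evaluable assessment before the first missed one. SAP 3.4.1 says that event and censoring dates follow Table 3.1 and applies the same censoring rules to iPFS. Protocol 7.2 schedules scans every 8 weeks (±3 days).

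**The concern.** The definition sentence and the derivation paragraph lead to different dates for the same patient. If confirmed events are dated at iCPD while an iUPD with no later scan is dated at the iUPD, one Kaplan-Meier curve mixes two dating conventions. A sequence of iUPD, iUPD, iCPD is worse served: SAP 3.4.1 asks for confirmation at the next assessment, whereas Appendix C allows it at a later one.

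For deaths, the definitions and the table classify one narrow group differently. If the definitions are followed, nothing says when those patients are censored, because the right-censoring sentences cover only patients who are alive without progression or lost to follow-up.

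SAP 3.4.2 plans Kaplan-Meier quartiles and 6- and 12-month rates for PFS and iPFS. With 6 planned patients, the handling of one patient is visible in those figures.

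**Working it through.** The documents give no event count or power for PFS or iPFS, so there is no planned figure to reproduce.

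**Inputs.** Months = (event date − first dose date + 1)/30.4375 (SAP 3.4.1). Confirmatory scan 4 to 8 weeks after iUPD (SAP 3.4 and Appendix C). Scans every 8 weeks (Protocol 7.2). Death limit 12 weeks = 84 days (SAP 3.4.1). Six planned patients (SAP 2.3.5). Scan weeks are nominal.

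**1. Shift when the first repeat scan confirms.** 28/30.4375 = 0.92 months; 56/30.4375 = 1.84 months.

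**2. Persistent iUPD: iUPD at week 16, iUPD at week 24, iCPD at week 32.**
- Initial iUPD: (112 + 1)/30.4375 = 3.71 months.
- The iUPD that is confirmed at the very next scan: (168 + 1)/30.4375 = 5.55 months.
- iCPD: (224 + 1)/30.4375 = 7.39 months.
- Spread: 112/30.4375 = 3.68 months.

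Protocol 7.2 covers directly only a progression confirmed at the repeat scan. It disregards one that is not confirmed and does not address persistent iUPD, so this sequence needs its own sentence.

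**3. Crossing the landmarks.** Six months falls at (6 × 30.4375 − 1)/7 = week 25.9. On scheduled scans confirmed at the first repeat, only a first progression at week 24 crosses it: 5.55 months at iUPD against (196 + 1)/30.4375 = 6.47 (week 28) to 7.39 (week 32) at iCPD. A first progression at week 16 confirmed 8 weeks later is still at 5.55. Twelve months falls at (12 × 30.4375 − 1)/7 = week 52.0. A first progression at week 48 is at (336 + 1)/30.4375 = 11.07 months, and confirmed at week 56 it is at (392 + 1)/30.4375 = 12.91.

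**4. Effect of one crossing (hypothetical event times).** Five other patients have events at weeks 8, 16, 32, 40 and 48, with no censoring. If the sixth event is at week 24, the 6-month rate is 3/6 = 0.500. If it is at week 28 or 32, the rate is 4/6 = 0.667. The difference is about 17 points.

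**5. Deaths by time since the last scan, 8-week schedule, no earlier progression or new therapy.**

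| Days since last scan | Definitions | Table 3.1 |
|---|---|---|
| up to 84 | event | event |
| more than 84, up to about 112 (one missed scan) | not an event, no date given | event at death |
| more than about 112 (two missed scans) | not an event | censored, date given |

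The upper edge is 2 × 56 = 112 days, or 109 to 115 days with the ±3-day window.

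**6. Effect of one such death on the 6-month rate (hypothetical event times; censoring dates assumed, since the SAP gives none).**
- Others at weeks 8, 16, 32, 40, 48; last scan week 8, death week 22. Counted: 3/6 = 0.500. Censored at week 8: 5/6 × 3/4 = 0.625. Censored at week 20 (12 weeks after the scan) or at death: 5/6 × 4/5 = 0.667.
- Others at weeks 8, 16, 24, 40, 48; last scan week 16, death week 30. Counted: 3/6 = 0.500. Censored at week 16: 5/6 × 4/5 × 2/3 = 0.444. Censored at week 28 or 30: 0.500.

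The effect can therefore go in either direction.

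**The case against.** The best reply is that the SAP read as a whole nearly answers both questions. On the event date, the derivation paragraph agrees with Protocol 7.2, leaving one definition sentence out of line. On deaths, the SAP names Table 3.1 as the source of dates, so the 12-week phrase looks like a leftover. Both observations are fair, and they indicate which way to correct the text. They do not remove the conflict, because the definitions still say something else.

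A reader might also infer more than the documents support:
- *That the borrowed PFS rule settles the date.* The SAP says "The iPFS time will be derived based on scan/assessment dates in the same manner as the PFS time derivation", and that rule is "Date of radiological progression will be determined based on the earliest assessment/scan dates of the component that triggered the progression (PD using RECIST"). It concerns scan dates within an assessment and is worded for RECIST progression. It does not choose between iUPD and iCPD.
- *That every death beyond 12 weeks is undated.* Table 3.1 dates deaths after two or more missed assessments. Only the one-missed-scan group is open. At the 6-week interval that SAP 3.4 uses after an unconfirmed iUPD, 2 × 42 = 84 days and the nominal gap closes.
- *That censoring after two missed scans is an error, or that the SAP departs from the protocol undeclared.* Protocol 9.2.1 counts death from any cause but leaves detailed censoring rules to the SAP. The text of SAP Section 6, on changes from the protocol, is not available here.
- *That RECIST PFS progression dates are affected.* They are not.

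The separate programming specifications (SAP Section 7) may resolve some of this but were not available.

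**Conclusion.** The point holds as a minor one: rules within the SAP, and between the SAP and Protocol 7.2, conflict as written. For iPFS, the literal definition dates a confirmed event 0.92 to 1.84 months later than Protocol 7.2, and the persistent-iUPD example has three possible dates spanning 3.68 months. For deaths, the conflict is confined to those more than 12 and up to about 16 weeks after the last scan on the 8-week schedule.

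The landmark-rate changes rest on hypothetical event times in 6 patients and, for deaths, on assumed censoring dates. They show possible size, not expected size. The weight is low: SAP 3.1 plans descriptive analysis, the study was terminated after Phase 1b (SAP Section 1), PFS and iPFS are not among the SAP 2.2 endpoints, and by-patient listings allow each case to be checked.

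**What to change.** In SAP 3.4.1:
1. State that a confirmed iPFS event is dated at the initial iUPD scan of the sequence that ends in iCPD, following the initial-scan principle of Protocol 7.2.
2. Reword the requirement for confirmation at the next assessment to match the persistent-iUPD rule in Appendix C, so that an iUPD, iUPD, iCPD sequence has one date.
3. Delete the 12-week limit on deaths from both the PFS and the iPFS definitions, so that Table 3.1 governs. Keeping the limit and adding a matching table row would also remove the conflict, but deletion is simpler because the SAP already names the table as setting dates.

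A sensitivity analysis counting all deaths, as in the Protocol 9.2.1 event definition, is optional. So is reconciling the 6-week interval in SAP 3.4 with the 8-week interval in Protocol 7.2.

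The cost is SAP wording and programming, with one descriptive table if the option is taken. iPFS times shorten only if they would otherwise have been programmed at iCPD. Results change for deaths only in the 12-to-16-week group, and only if the definitions would otherwise have been programmed.
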